6.2 Secondary Endpoint (anhedonia as measured by the SHAPS)

Differential change over time between those who receive BATA and those who receive MBCT

6.3 Evaluation Of Adverse Events

The study monitors will be the PIs. They will ensure the quality of the study and establish that the study staff is complying with the investigational plan and IRB regulations. Throughout the investigation, the monitors

will ensure that the facilities being used continue to be acceptable for the purposes of the study, that the investigational plan is being followed, that any changes to the protocol have received IRB approval and have been reported to the sponsor, and that accurate, complete, and timely reports are made to the IRB. They will confirm that inclusion and exclusion criteria have been met for each subject enrolled, and compliance with all other aspects of the investigational plan are met. They will safeguard against and regularly monitor for unanticipated problems by ensuring appropriate oversight of all study and treatment procedures. A weekly joint UNC/Duke study team meeting will be conducted to discuss research procedures.

Per NIH requirements for multi-site clinical trials, the trial will be monitored by an independent Data Safety Monitoring Board (DSMB). The DSMB for this study is the BATA DSMB. The BATA DSMB will meet biannually to review all aspects of this study. The study staff will prepare biannual reports for the DSMB on participant accrual, safety events, clinical outcomes, and adherence/drop outs. All Serious study related adverse events will be submitted to the DSMB safety officer within 4 weeks of the event, as will any concerns regarding confidentiality. Non-serious AEs will be included in the biannual reports.

The goals of this DSMB are:

- 1) To review and report adverse events (see schedule below).
- 2) To monitor the level of risk posed by the study and insure that risks are minimized.
- 3) To review modifications to risk management protocols.
- 4) Review progress toward meeting enrollment goals.
- 5) To review procedures for maintaining the confidentiality of data, and quality of data collection, management, and analyses.
- 6) Serve as final arbiters of whether individual subjects should be removed from a protocol.
- 7) To recommend continuation, discontinuation, modification, or termination of a study based on emerging data (in the study and literature) and evaluation of risk/benefit ratio.

Data type	Frequency of review by study team	Frequency of report to DSM team
Participant accrual	Weekly	Biannually
Study adherence and dropouts	Weekly	Biannually
Adverse events	As events occur	Any serious, study related events (< 4 weeks); nonserious, related AEs reported biannually
Participant confidentiality	As events occur	As events occur (< 4 weeks)

The options available for the outcome of DSMB review are:

- Recommend continuation with no modification,
- Recommend continuation with no modification(s) to the protocol but with other recommendations (e.g., modify informed consent form, seek additional expert review), Recommend continuation with modification(s) to protocol,
- Recommend suspension of enrollment pending additional information,
- Recommend suspension of all study activities pending additional information,
- Recommend termination of study because of undue safety risks to subjects,
- Recommend termination of study or part of the study because of results of formal interim analyses.

In the event that the DSMB recommends stopping the study early or making a major modification to the protocol, the DSMB Chairperson should provide a brief rationale behind the decision. Recommendations for stopping or modifications should be accompanied by the minimum amount of information required for the study PIs to make a reasoned decision about the recommendation, and the rationale for such recommendations should be as clear and precise as possible.

After each participant is scanned, the PI will communicate with the UNC BRIC Director, to review any unanticipated problems (including but not limited to adverse events) to monitor subject safety. We will immediately alert the IRB if any concerns arise. We will safeguard against and regularly monitor for unanticipated problems by ensuring appropriate oversight of all study and treatment procedures by the PI. A weekly team meeting will be conducted to discuss research procedures.

Quality assurance. The Duke and UNC study teams will meet weekly to review any research issues that may have arisen during the past week as well as to monitor progress on subject recruitment and other research-related matters. Additional meetings are conducted on an as-needed basis.

The following guidelines will be used to describe the severity of any adverse events that occur:

- Mild – Events require minimal or no treatment and do not interfere with the participant’s daily activities.
- Moderate – Events result in a low level of inconvenience or concern with the therapeutic measures. Moderate events may cause some interference with functioning.
- Severe – Events interrupt a participant’s usual daily activity and may require systemic drug therapy or other treatment. Severe events are usually potentially life-threatening or incapacitating. Of note, the term “severe” does not necessarily equate to “serious”.]

All adverse events (AEs) must have their relationship to study intervention assessed by the clinician who examines and evaluates the participant based on temporal relationship and his/her clinical judgment. The degree of certainty about causality will be graded using the categories below. In a clinical trial, the study product must always be suspect.

Related – The AE is known to occur with the study intervention, there is a reasonable possibility that the study intervention caused the AE, or there is a temporal relationship between the study intervention and event. Reasonable possibility means that there is evidence to suggest a causal relationship between the study intervention and the AE.

Not Related – There is not a reasonable possibility that the administration of the study intervention caused the event, there is no temporal relationship between the study intervention and event onset, or an alternate etiology has been established.

The PI will be responsible for determining whether an adverse event (AE) is expected or unexpected. An AE will be considered unexpected if the nature, severity, or frequency of the event is not consistent with the risk information previously described for the study intervention.

The occurrence of an adverse event (AE) or serious adverse event (SAE) may come to the attention of study personnel during study visits and interviews of a study participant presenting for medical care, or upon review by a study monitor. Protocol violations that could represent serious or continuing noncompliance will be brought to the attention of the PI as soon as possible and not longer than 24 hrs. These violations will be reported to the IRB using the appropriate documentation within 5 days of notification of the PIs. If these events are determined to be serious or continuing noncompliance by the Duke IRB, they will then be reported to the overall sponsor, NIMH, within 10 business days and entered on the study log. They will be reported to the DSMB <4 weeks.

In this study we will use the FDA's definition of adverse events (AEs) and serious adverse events (SAEs). It is not expected that any such AEs or SAEs will occur in this experiment. However, AEs and SAEs will be assessed by a trained study coordinator, study therapist or other approved study team member, and discussed at the weekly research staff meetings. We will start collecting AEs/SAEs at the pre-treatment PET visit at UNC's BRIC and will continue to collect them through their final visit. All follow-up AEs/SAEs will end at their final study visit.

Any SAE during this collection period will be brought to the attention of the PI as soon as possible and not longer than 24 hrs. Any SAE (regardless of the study relatedness), will be reported to the Duke University Medical Center Institutional Review Board using the appropriate documentation within 5 days of the event. Unexpected study related SAEs will be reported to the overall sponsor, NIMH within 10 business days. This will be the responsibility of the PI. The UNC IRB will decide as to whether additional reporting requirements are needed.

Non-serious AEs that are deemed study related will be reported to the IRB and overall sponsor with annual reporting and entered on the subject's individual adverse event page in REDCap. These will be reported to the DSMB as per the DSMB scheduled reporting.

Protocol deviations around study visit windows, skipped questions on self-report measures, missed therapy sessions, etc. will not be reported to the UNC IRB. Other protocol deviations will be reported to the PIs upon discovery and will then be reported to UNC IRB within 2 weeks. These deviations will in turn be reported to NIMH annually within the study progress report and reported to the DSMB per the DSMB designated meeting schedule.

In this study, if a subject experiences an SAE or study related, non-serious AE and they are not resolved at their final study visit, because it is a minimal risk study, we do not plan to continue to follow the event past their final study visit.

Reporting of non-study related, non-serious AEs are not reported to the IRB, overall sponsor, and not entered on the study AE tracking log, however they will be entered on the subject's individual adverse event pages within REDCap and checked at every study visit.

The study clinician will immediately report to the sponsor any serious adverse event, whether or not considered study intervention related, and must include an assessment of whether there is a reasonable possibility that the study intervention caused the event. Study endpoints that are serious adverse events (e.g., all-cause mortality) must be reported in accordance with the protocol unless there is evidence suggesting a causal relationship between the study intervention and the event (e.g., death from anaphylaxis). In that case, the investigator must immediately report the event to the sponsor.

All serious adverse events (SAEs) will be followed until satisfactory resolution or until the site investigator deems the event to be chronic or the participant is stable. Other supporting documentation of the event may be requested by the Data Coordinating Center (DCC)/study sponsor and should be provided as soon as possible.

Protocol violations that could represent serious or continuing noncompliance will be brought to the attention of the PI as soon as possible and not longer than 24 hrs. These violations will be reported to the IRB using the appropriate documentation within 5 days of notification of the PIs. If these events are determined to be serious or continuing noncompliance by the Duke IRB, they will then be reported to the overall sponsor, NIMH, within 10 business days and entered on the study log. They will be reported to the DSMB <4 weeks.

Adverse events will be reported to the study Data Safety and Monitoring Board (DSMB). The members of the DSMB will be responsible for safeguarding the interests of study participants, assessing the safety of all study procedures, and shall monitor the overall conduct of the study. This Committee will serve as an independent advisory group to the study investigators and will provide recommendations about starting, continuing, and stopping the *BATA Study*. The Committee serves the following functions:

- Review the research protocol and plans for data and safety monitoring, including all proposed revisions;

- Review methodology used to maintain confidentiality of the study data and results of monitoring by reviewing procedures put in place by investigators to ensure confidentiality;
- Monitor study design and procedures to maximize safety and minimize risk of subjects;
- Evaluate study progress, including periodic assessments of data quality and timeliness, participant recruitment, accrual and retention, participant risk versus benefit, performance of the study site(s), and other factors that may affect study outcome;
- Consider factors external to the study when relevant information becomes available, such as scientific or therapeutic developments that may have an impact on the safety of the participants or the ethics of the studies;
- Review serious adverse event documentation and safety reports and make recommendations regarding protection of the safety of the study participants;
- Report to the IRBs on the safety and progress of the study (via periodic reports to be provided by the two Sites to their respective IRBs);
- Evaluate and report to the IRBs on any perceived problems with study conduct, enrollment, sample size, and/or data collection;
- Provide to the IRBs a recommendation regarding continuation, termination or other modifications of the study based on the cumulative experience including the observed beneficial or adverse effects of the treatment under study;

This Committee will be responsible for identifying mechanisms for the completion of various tasks that would impact the safety and efficacy of all study procedures and overall conduct of the study. The table below identifies the key areas for which oversight will be necessary and the ways in which the Committee will complete those tasks.

Basic Responsibility of DSMB	Method BATA Study DSMB will use to complete task
Monitor adverse events	Review SAE updates as provided by the Study Team per the Study Protocol. Serious, study related events, as well as concerns regarding confidentiality, will be reported to the DSMB within 4 weeks.
Monitor data quality	Review periodic reports
Oversee recruitment and enrollment	Review periodic reports
Ensure proper reporting	Periodic reports from the Study Team, initially to occur every 6 months, subsequently to occur at an interval specified by DSMB request.
Recommend study disposition	Provide recommendations for study status after periodic reviews, as outlined in this Charter

6.4 Statistical Methods

Aim 1, fMRI outcomes: Only patients who complete at least two therapy sessions will participate in post-treatment assessments. We will compare fMRI activation in regions of interest at pre- and post-treatment. The design is a 2 (BATA vs MBCT) X 2 (CN, rACC) X 2 (pretreatment vs post-treatment) ANCOVA testing the change from pre- to post-treatment as moderated by treatment group and brain region in the outcome variables. The Treatment × Time interaction beta will be used to evaluate whether BATA produces changes in neural responses to reward anticipation and reward outcomes that exceed our *a priori* target engagement criteria (increased right caudate nucleus (CN) activation during reward anticipation and decreased rostral anterior

cingulate cortex (rACC) activation during reward outcomes) and exceed changes due to MBCT. *Post-hoc* comparisons will compare change across each region.

Aim 2, anhedonia outcomes: To evaluate the effects of BATA, relative to MBCT, for on anhedonia symptoms treating anhedonia, we will test for differential change over time between those who receive BATA and those who receive MBCT post-treatment. We will use an intent-to-treat (ITT) analysis for patients who receive BATA relative to those who don't. The ITT model will be a repeated-measures ANCOVA with effects for treatment condition (BATA, MBCT), outcome measure (SHAPS), time (pre-treatment, post-treatment) and their interactions. The interaction tests will assess mean differences at each time point as well as differences in the degree of change between the groups. This also provides tests of each group relative to their baseline scores. We will include gender and age as covariates in these models.

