Test Article(s) (If Applicable)	
Behavioral Activation Treatment for Anhedonia (BATA): We have modified Behavioral Activation Treatment for Depression to create Behavioral Activation Treatment for Anhedonia (BATA) which we will evaluate in this study by comparing its effects on brain functioning relative to treatment with Mindfulness-Based Cognitive Therapy (MBCT).

Study Design	Following a phone/online screen and an initial assessment session to confirm eligibility, participants will complete a baseline fMRI session at the UNC Biomedical Research Imaging Center (BRIC). They then will be randomized to receive a 15-week course of BATA (50%) or a 15-week course of Mindfulness Based Cognitive Therapy (MBCT) (50%) administered at Duke University Medical Center (DUMC). Both groups will receive pre- and post-treatment scans as well as two mid-treatment scans (weeks 8 and 12) to evaluate treatment BATA dose.
---------------------	--

Subject Population	Inclusion Criteria
key criteria for Inclusion and Exclusion:	
 1. 18-50 years old and treatment seeking; 2. SHAPS scores ≥ 20, corresponding to clinically significant anhedonia; 3. Clinician's Global Impression Scale-Severity score (CGI-S) ≥ 3 to assure a clinically impaired sample; 4. Seeking treatment for anhedonia (i.e., referred from an outpatient clinic or responded to an advertisement for anhedonia treatment; endorses desire for treatment during screening).

Exclusion Criteria

5. Those for whom medication management is the primary gold-standard treatment, including those with bipolar disorder/mania, schizophrenia spectrum, and other psychotic disorders;
6. Prior treatment with behavioral activation therapy for depression or mindfulness-based treatments (those with exposure to other forms of psychotherapy, e.g., supportive therapy, will be eligible);
7. Those who may have difficulty understanding the cognitive components of BATA, including those with intellectual disability, neurocognitive disorders, and dissociative disorders;
8. Feeding and eating disorders which may have confounding effects on the BOLD fMRI signal;
9. Substance Use Disorders given confounding effects of substances of abuse on the BOLD fMRI signal;
10. Suicidal intent and plan;

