11. Psychotropic medication use in the past 4 weeks (8 weeks for fluoxetine) and/or current psychotherapy. Participants must be medication-free at study entry; study personnel will not supervise medication taper for the purpose of the study, but those who taper under the supervision of their regular provider will be eligible;
12. Currently pregnant, as measured by urine pregnancy screen immediately before MRI scans;
13. Positive urinalysis screen for cocaine, marijuana, opiates, methadone, amphetamines, and benzodiazepines (conducted on-site via Biosite Triage Meter Plus) at study entry.
14. No neurological conditions (e.g., history of stroke, seizure, or TBI);
15. Contraindications for 7T imaging (criteria are more stringent than for 3T imaging): Metal in the body, dental work that is not fillings or gold, any tattoos, any metal in the body, any metal injury – especially those to the eyes, any other type of implant unless they are 100% plastic.

Number Of Subjects	60 subjects will be randomized such that half will receive BATA and half will receive MBCT.
---------------------------	---

Study Duration	Approximately 16 weeks
Study Phases	(1) Phone/online Screening : initial screening for eligibility.
Screening	(2) In-Person Screening : further screening for eligibility and consent
Study Treatment	(3) Baseline fMRI
Follow-Up	(4) Initiate up to approximately 15 weeks of therapy (experimental treatment (BATA) or comparison treatment (MBCT)) (5) Mid-treatment fMRI scans at approximately weeks 8 and 12. (6) Post-treatment fMRI scan.
Efficacy Evaluations	(1) fMRI activation in right CN during reward anticipation and rACC during reward outcomes (2) Anhedonia severity (SHAPS scores)
Pharmacokinetic Evaluations	N/A
Safety Evaluations	1) 7T MRI safety screening form completed before each scan session 2) Columbia-Suicide Severity Rating Scale (C-SSRS) completed if a subject endorses suicidal thoughts at therapy visits.

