4.8 Screen failure procedures

If more than 4 weeks elapse between the baseline screen and the first scan session, this will be considered a screen fail and the individual will not be randomized.

5 STUDY EVALUATIONS AND MEASUREMENTS (how measurements will be made)

1) fMRI data (primary endpoint) will be collected at the UNC Biomedical Research Imaging Center (BRIC) at week 0, week 8, week 12, and week 15. Analyses of fMRI target engagement will focus on activation in the right CN during reward anticipation, the rACC during reward outcomes, and bilateral amygdala in response to threat. Data will be preprocessed using FSL (Oxford University, UK). We will ensure groups do not differ in head motion by calculating mean framewise displacement which yields, for each participant, a value indicating mean head displacement from one volume to the next. Hypotheses will be evaluated with a ROI approach whereby signal intensities are extracted from ROIs for the relevant task contrasts (i.e., potential win versus non-win trials during MID reward anticipation trials; wins versus non-wins during MID reward outcome trials; fearful and angry faces > shapes during the threat task). ROI analyses will be followed-up with whole-brain analyses that will yield activation maps thresholded at a False Discovery Rate of 0.01 to allow for an examination of activation in other reward processing regions, including the ventral striatum/nucleus accumbens, putamen, ventral tegmental area, and orbitofrontal cortex. To optimize BOLD signal coverage in the ventral

tegmental area we will acquire high-resolution T1-weighted images with 1x1x1 mm voxel size to allow for precise registration and will use cardiac and respiratory gated imaging during the acquisition of structural scans to address pulsatile artifacts using retrospective corrections implemented with the FSL PNM toolbox.

2) The Snaith–Hamilton Pleasure Scale (SHAPS) is a measure of anhedonia used to verify inclusion criteria. It is a well-validated 14-item self-report questionnaire that is administered by computer.

3) DSM diagnoses will be made using the SCID5, a semi-structured patient interview, and will be used to verify inclusion criteria

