6.5 Sample Size and Power

Power Analyses: In this study we will enroll 60 participants, whom will receive BATA treatment MBCT treatment. Based on our pilot data demonstrating increased right CN activation during reward anticipation and decreased rACC activation during reward outcomes, we calculated an effect size of approximately $z=4.1$. Conservatively, we estimate the effect size for the increased right CN activation and reduced rACC activation will be in the range of $z = (0.75-1.25)$. Our models thus have >90% power at $\alpha=0.025$.

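### Scans and SHAPS are collected at four visits, but the stated models use only pre and post: the week 8 and 12 scans have no analysis, and a patient without a final scan contributes no change

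*Combined protocol and SAP*

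**What the plan says.** Section 5 lists the primary-endpoint fMRI data, which "will be collected at the UNC Biomedical Research Imaging Center (BRIC) at week 0, week 8, week 12, and week 15". Section 4.2 confirms that both arms are scanned at weeks 8, 12 and 15, and that SHAPS is completed before treatment, at weeks 8 and 12, and after treatment. The synopsis (Study Design) describes "two mid-treatment scans (weeks 8 and 12) to evaluate treatment BATA dose".

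The Aim 1 analysis in section 6.4, repeated in the synopsis, reads "We will compare fMRI activation in regions of interest at pre- and post-treatment", and its model has two time levels: "The design is a 2 (BATA vs MBCT) X 2 (CN, rACC) X 2 (pretreatment vs post-treatment) ANCOVA". The Aim 2 model for SHAPS, labelled intent-to-treat, also has only pre-treatment and post-treatment as levels of time. Nothing in section 6 uses a week 8 or week 12 measurement, and neither aim in section 2 poses a dose question.

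The plan gives no missing-data method, no expected dropout rate and no allowance for loss in the sample size. Section 4.7 defines a dropout by consecutive missed appointments and says the definition will be used in analysis, but not how. Section 6.4 restricts post-treatment assessment to patients with at least two therapy sessions.

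**The concern.** There are two problems.

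First, the mid-treatment scans have a stated purpose and no analysis. Of 60 x 4 = 240 planned scans, up to 60 x 2 = 120 appear in no model. Whatever is later done with them will be chosen after the data are seen.

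Second, a pre-to-post comparison needs the final scan. The protocol has several routes by which a patient could have mid-treatment scans but no final one: missed appointments (4.7), starting a psychotropic drug (4.5), worsening or suicidality (1.3), and distress or a positive pregnancy test at a scan (5.3). Worsening and starting medication are plausibly related to response. The week 8 and 12 measurements record that early response, and the stated models ignore them. At stake is the estimate of the Treatment x Time effect, the trial's primary result.

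**Working it through.** **The plan's power figure, for reference.** Section 6.5 gives 60 patients, effect sizes of 0.75 to 1.25 labelled z, alpha 0.025 and power above 90%. The synopsis gives equal allocation, so 30 per arm. The metric is undefined; I read it as a standardized between-arm difference in change, tested two-sided. The SE is sqrt(2/30) = 0.258.
- 0.75: 0.75/0.258 - 2.241 = 0.66, power 74.6%.
- 1.0: power 94.9%. 1.25: power 99.5%.

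The stated figure is therefore not reproduced at the low end of the range (82.8% if one-sided). That is a separate matter, and this point does not depend on it.

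**Bias from losing final scans.** Everything here except the 0.75 is an assumption: unit variance at each scan, equal correlation r between any two scans, true difference 0.75. Write B, W and P for the baseline, week 8 and post-treatment values.
- Cov(P - B, W - B) = r - r - r + 1 = 1 - r, and Var(W - B) = 2(1 - r). The slope of final change on week 8 change is 1/2.
- If loss raises the mean week 8 change among completers by k SDs in an arm, completer change in that arm is off by (1/2) x k x sqrt(2(1 - r)).
- The between-arm bias is (1/2) x (k in BATA - k in MBCT) x sqrt(2(1 - r)).

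With dropout logistic in week 8 change and losses of 10% and 30%, a gap in k of about 0.2 corresponds to the simulated results. The bias is then 0.1 x sqrt(2(1 - r)): 0.118, 0.100 and 0.077 at r = 0.3, 0.5 and 0.7. Added to 0.75 this gives 0.87, 0.85, 0.83; subtracted, 0.63, 0.65, 0.67. Large-sample simulation agrees to within 0.01:

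| Loss pattern (r 0.3 to 0.7) | Completer change | Likelihood using mid-treatment data |
|---|---|---|
| On week 8 change, 10% MBCT / 30% BATA | 0.83-0.87 | about 0.75 |
| Same, split reversed | 0.64-0.67 | about 0.75 |
| On week 8 change, 20% in each arm | 0.75 | about 0.75 |
| On week 8 level, 10% MBCT / 30% BATA | 0.75 | about 0.75 |

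The third row is unbiased because the two k values cancel. The fourth is unbiased because Cov(P - B, W) = r - r = 0.

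That last cancellation is special to equal correlations. If correlation instead decays at 0.7 per 4 weeks, Cov(P - B, week 12) = 0.7^0.75 - 0.7^3 = 0.765 - 0.343 = 0.42. Loss of poor week 12 responders in BATA only then gives completer change of 0.87 at 20% loss and 0.93 at 30%. A likelihood model with only two visits gives 0.95 and 1.04; the four-visit model gives 0.75. Calling the two-visit analysis a mixed model therefore does not cure the problem.

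**Precision.** Assume late loss, half after week 8 and half after week 12, with equal correlations of 0.3-0.7 or serial decay of 0.5-0.85 per 4 weeks. Power is for 0.75 at two-sided 0.025:

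| Loss | Effective N, pre/post | Effective N, four visits | Power, pre/post | Power, four visits |
|---|---|---|---|---|
| 10% | 54 | 54.4-57.1 | 69.6% | 70.0-72.3% |
| 20% | 48 | 48.7-54.0 | 63.9% | 64.6-69.6% |
| 30% | 42 | 42.9-50.6 | 57.5% | 58.5-66.5% |

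**The case against.** The best case for the plan has four parts.

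1. It never says that patients are dropped; it is silent on missing data. A reader might infer that everyone who stops therapy leaves the analysis. The documents do not support that: section 6.4 implies that a patient with at least two sessions can still have the final scan. This stands. The loss at issue is a missing final scan, and its size is unknown.

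2. A reader might infer that the pre-post estimate is valid only if dropout is unrelated to response, or that it will exaggerate the benefit of BATA. Neither follows. Equal response-related loss in both arms leaves it unbiased in the check above, and reversing the split reverses the sign. If ANCOVA means adjustment for baseline, the 10%/30% case reads 0.79-0.81 among completers, a smaller bias. This stands too.

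3. A reader might take week 8 and week 12 contrasts as the missing dose evaluation. The number of sessions received is not randomized, so these contrasts describe time course and only partly address dose.

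4. Neither aim asks about dose, so one sentence naming an exploratory analysis would close that gap. True, but it would leave the missing final scans unaddressed, when data already collected can reduce the problem.

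**Conclusion.** The point holds. It is a matter of record that four visits are collected and two are modelled, for both fMRI and SHAPS, and that the stated dose purpose of the mid-treatment scans has no matching analysis. The possible bias is conditional: it needs loss of final scans that differs between arms and is tied to early response. In the scenarios shown, a true 0.75 reads 11-16% too high (0.83/0.75 to 0.87/0.75), 11-15% too low (0.67/0.75 to 0.64/0.75), or correct. The documents give no dropout rate, correlation or mechanism, so neither size nor direction can be predicted.

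The four-visit result of about 0.75 holds because the assumed loss depends only on observed measurements. It offers little for patients lost before week 8 and no guarantee if loss depends on unobserved outcomes. Precision is a minor reason for the change: power rises by about 0.4 to 9 points at 10-30% loss. The change should be made, but the trial does not fail without it.

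**What to change.** - **Primary model.** Fit a linear mixed model to all four scans with treatment, visit as a category, treatment x visit and the SHAPS randomization stratum, with unstructured covariance. Either keep region and its interactions as in section 6.4, or fit each ROI separately at the 0.025 level used in section 6.5, and say which. One ROI needs 4 x 5/2 = 10 covariance parameters. Keeping both regions needs 8 x 9/2 = 36, so name a simpler fallback structure for that option.
- **Primary contrast.** Keep the post-treatment treatment contrast, so the primary question does not change.
- **Missing data.** State the missing-at-random assumption and prespecify one sensitivity analysis that departs from it, for example by shifting the unobserved final values over a range.
- **Mid-treatment scans.** Prespecify the week 8 and week 12 contrasts as a secondary description of time course, not a randomized dose comparison, and align the synopsis wording with that.
- **SHAPS.** Use the same four-visit model, keeping age and gender as covariates.
- **Final scan.** State that patients who stop therapy after at least two sessions are still scanned post-treatment, as section 6.4 implies, subject to the scan-safety rules already in the plan.

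The cost is SAP wording and a little more analysis work. No new data are needed.
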